6.1.3 Pregnancy and breastfeeding

For female subjects with childbearing potential (they have had at least one period during the last 12 months), a urine pregnancy test will be performed at the inclusion visit, to ensure that the subject is not pregnant. The urine pregnancy test will be performed by dip-stick at the trial site. Furthermore, the female subjects should not be breastfeeding, when participating in the clinical investigation.

Example: As a minimum, Investigator must talk to the women about the risk of and how to avoid unwanted pregnancy at inclusion and at every test period the subject participates in hereafter.

If the subject is sexually active, she should be willing to practice appropriate contraceptive methods until the end of the investigation. Appropriate contraceptive methods are: sexual abstinence (in some cases when the women are older than 50 years, but are not yet post-menopausal, the investigator may evaluate that it is not reasonable to ask these women to start using safe contraceptives for the duration of the investigation); oral contraceptives, trans dermal patches or depot injection of a progestogen drug, double barrier method: condom or occlusive cap (diaphragm or cervical/vault caps) plus spermicidal agent; intrauterine device (IUD), intrauterine system (IUS), implant, or vaginal ring (placed at least 4 weeks before the first test period); or male partner sterilization before the female participant's entry into the investigation and is the sole sexual partner for that female participant. However, national requirements should always be followed.

If the subject becomes pregnant during the investigation, it is important, that the subject informs the Investigator/Investigator representative immediately. The medical adviser will then consider whether she should continue in the investigation.

6.2 Recruitment and enrolment

6.2.1 Recruitment process

The recruitment of potential subjects will commence only once authorisation has been received from the Regulatory Authorities (if applicable) and EC approval. The recruitment period from first subject enrolled to last subject enrolled is expected to be approximately 4 months. Recruitment will be competitive.

Table 1. Overview of the recruitment process

Recruitment method	Outpatient clinic/hospital	Advertising	Coloplast Database
Potential subjects	Recruitment will go through the outpatient clinic/ hospital site. Potential subjects are qualified by the inclusion criteria described in section 6.1.1	Recruitment will go through advertising in relevant channels of online and offline media (e.g., posters, social media, online paid media etc.). For the online channels, potential subjects will be directed to a landing page with a self-screener that qualifies the subjects in accordance with the inclusion criteria described in section 6.1.1 For the offline channels, study duration and screening criteria will be listed, and subjects are encouraged to contact the PI for further information.	Recruitment will go through the Coloplast database, where potential subjects are contacted by email. Subjects are selected according to the inclusion criteria described in section 6.1.1 and include: age, gender, product usage, type, size, and permission status. If the subjects are interested, they will be directed to a landing page, where eligibility is confirmed through a self-screener that qualifies subjects in accordance with the inclusion criteria.
First contact	Potential subjects will be contacted by email, phone call or contacted during a planned visit in the outpatient clinic at the hospital. If a subject is eligible and interested in participating in the investigation upon a short introduction, then written information about the investigation (Subject Information Form/Informed Consent Form) will be distributed to the subject. The Principal Investigator or delegate will invite the subject to a Screening Visit (V0).	Potential subjects will be directed via the advertisement to a landing page with a self-screener. If a subject qualifies for the study, telehealth nurses will call the subject to verify eligibility. A list of all eligible subjects is sent to site, where a final screening call is conducted to reconfirm eligibility. If subjects qualify and are interested in participating, a date for V0 is agreed and written information about the investigation (Subject Information Form/Informed Consent Form) is sent to the subject.	Potential subjects from the database will be contacted by email. Potential subjects via the emails be directed to a landing page with a self-screener, and if a subject qualifies for the study, telehealth nurses will call the subject to verify eligibility. A list of all eligible subjects is sent to site, where a final screening call is conducted to reconfirm eligibility. If subjects qualify and are interested in participating, a date for V0 is agreed and written information about the investigation (Subject Information Form/Informed Consent Form) is sent to the subject.
Screening visit (V0)	At the scheduled Screening Visit (V0) the Principal Investigator or delegate will introduce the investigation and review the inclusion and exclusion criteria. If the subject wishes to reconsider her participation at V0, the subject has the right to wait a minimum of 24 hours before deciding on participation. If the subject hereafter decides to participate in the clinical		

Recruitment method	Outpatient clinic/hospital	Advertising	Coloplast Database
	
investigation a Baseline Visit (V1) will be scheduled unless performed the same day as the Screening Visit.
 
The Screening Visit can be performed at the site or as a phone call. If the subject does not meet the inclusion criteria or meets the exclusion criteria, this will be registered at the Subject Pre-Screening Log.
		
Baseline visit (V1)	
If the subject decides to participate and it is certain that it is understood what the investigation entails, the subject will be asked to sign the SIF/ICF. When the SIF/ICF is signed, the subject is considered included in the investigation.
		

6.3 Subject withdrawal criteria

The subject is allowed to withdraw from the investigation at any time for whatever reason without any consequences for their future treatment outside the clinical investigation. The principal investigator may withdraw a subject from the investigation at any time if they judge it to be the subject's interest.

The principal investigator must withdraw a subject from the investigation due to:

- Noncompliance with the CIP impacting the scientific integrity of the investigation.
- If a subject's safety and wellbeing is compromised by further participation.
- Subjects lost to follow-up. At least three documented attempts will be made to verify subjects lost to follow-up.

Randomized subjects that for some reason withdraw from the clinical investigation can be replaced.

Replacements should be discussed with Sponsor. Please also refer to section 10.7 Sample size for further information.

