6.4 Screening Failures and Drop-Outs

Subjects that have signed the informed consent form but fail to comply with inclusion or exclusion criteria are considered "screening failures" up until randomisation. After randomisation subjects who fail to comply with inclusion or exclusion criteria will be withdrawn from the study and considered "drop-outs"

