10.2 Definition of analysis populations

Screening Failures (SF), Intention to Treat (ITT), Full Analysis Set (FAS), Safety and Per Protocol (PP) analysis set will be defined at a formal data review meeting prior to database lock. As a minimum, the data manager, the clinical manager, and the statistician will be involved in the classification of subjects.

Subjects not adhering to inclusion and/or exclusion criteria are considered screening failures (SF) and are not included and randomised.

- The Safety population will constitute all subjects included i.e. subjects who have given informed consent and fulfils the in- and/or exclusion criteria.
- The ITT population will constitute all randomised subjects.
- The full analysis set is a modified ITT population i.e., a sub-population of the ITT population, and will constitute all randomised subjects, who have been exposed to at least one device, with at least one endpoint recorded (data non-missing).
- The PP is a sub-population of the full analysis set where all subjects have received treatment as per protocol.

Individual endpoints/data points may be excluded from the analysis, even though the corresponding subject belongs to any of the pre-defined populations. Exclusion of subjects or data points must be documented.

All statistical analysis and test of hypothesis will be based on the full analysis set, and in addition, primary endpoint will also be analysed in the PP population, whereas adverse events and device deficiencies will be assessed in the safety population.

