10.7 Sample size

Input for the sample size calculations i.e., means and standard deviations are based on three exploratory studies CP322, CP323 and CP324. The studies investigated earlier prototypes of the micro-hole catheter with identical or similar endpoints in populations of both IC users and healthy volunteers.

A sample size for the primary endpoint of residual urine at 1st flow-stop (RV1) is judged to be accommodated by 60 subjects with a power of ~ 90%, assuming a difference of 15 mL, a $sd_{comparator}$ of 50 mL and a sd_{active} of 15 mL (please see Table 3).

Table 3. Sample size calculation of Residual urine at 1st flow-stop in a cross-over design, solving for varying power and number of subjects, assuming no within subject correlation as a worst-case approach, using proc Power in SAS.

μ (sd) comparator	μ (sd) active	Alpha	Power	Sample size
25 (50)	10 (15)	0.05	71.9 %	40
25 (50)	10 (15)	0.05	81.2 %	50
25 (50)	10 (15)	0.05	87.7 %	60
25 (50)	10 (15)	0.05	92.2 %	70

Taken into consideration a discontinuation of 20%, the endpoint of RV1 is sufficiently supported by randomising at least 72 subjects.

If the number of subjects contributing to the primary analysis is less than 60 subjects, it must be carefully considered to include additional subjects (subjects replaced), to maintain sufficient power in the primary analysis.

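### Section 6.3 makes withdrawal mandatory for noncompliance judged to affect scientific integrity, and nothing in the plan keeps the withdrawn woman for her remaining V2/V3 measurement

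*Combined protocol and SAP*

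**What the plan says.** Section 6.3 opens its list with "The principal investigator must withdraw a subject from the investigation due to" and gives three grounds. The first is "Noncompliance with the CIP impacting the scientific integrity of the investigation"; the others are compromised safety or wellbeing, and loss to follow-up. The investigator has no discretion once the first ground is judged to be met, and the section does not say what counts as an effect on scientific integrity.

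The same section states: "Randomized subjects that for some reason withdraw from the clinical investigation can be replaced". It adds a condition, "Replacements should be discussed with Sponsor", and points to section 10.7. That section asks that additional subjects be considered "If the number of subjects contributing to the primary analysis is less than 60 subjects".

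Section 10.2 states that "All statistical analysis and test of hypothesis will be based on the full analysis set". The FAS requires randomisation, exposure to at least one device and at least one recorded endpoint; it does not require both visits. On adherence, "The PP is a sub-population of the full analysis set where all subjects have received treatment as per protocol". Section 10.2 also allows single data points to be left out, with documentation.

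Section 10.3 analyses RV1 in a linear mixed model with subject as a random component and visit and device as fixed effects. The two sensitivity analyses are the PP run and a Wilcoxon signed rank test. Section 10 states no missing-data assumption and plans no sensitivity analysis for missing data.

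The title calls the study open-labelled. Section 5.9 lists the subjects, the nurses and several sponsor roles as unblinded. It does not name the principal investigator, but nothing in it blinds that role.

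**The concern.** A judgement made after randomisation, with the device known and against an undefined threshold, can decide whether a woman is measured at V2 or V3. If that judgement is related to the device or to how well she empties, the comparison loses observations selectively.

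The removal is also unnecessary for the primary question. RV1 comes from a catheterisation by an HCP in the clinic, and deviations at home do not usually prevent it. The plan already has three ways of dealing with noncompliance that do not remove the subject: deviation reporting in section 13, the PP set in section 10.2, and documented exclusion of a single spoilt data point in section 10.2. Section 6.3 adds a fourth that cannot be undone, because an observation never made cannot be recovered in analysis.

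At stake are the completeness of the paired RV1 data and the credibility of the superiority conclusion.

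**Working it through.** The plan attaches no figure to the withdrawal rule, so the check is mainly a comparison of sections, with some arithmetic.

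**1. What each withdrawal costs.** RV1 by HCP is taken once at V2 and once at V3 (sections 5.1 and 5.2).

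| Withdrawn | RV1 values obtained | Mixed model | Wilcoxon signed rank |
|---|---|---|---|
| Before V2 | 0 of 2 | contributes nothing | out |
| Between V2 and V3 | 1 of 2 | contributes V2 | out |
| Not withdrawn, both visits attended | 2 of 2 | contributes both | in |

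**2. How the plan treats the same noncompliance elsewhere.**
- Section 13: report it, grade it minor or major, record whether it affects data integrity. Neither grade leads to withdrawal.
- Section 10.2: leave the subject out of the PP set; she stays in the FAS.
- Section 6.3: remove the subject from the investigation.

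The first two are compatible with continued measurement; the third is not.

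**3. Is replacement a remote possibility?** Section 10.7 gives 60 subjects, 20% discontinuation and 72 randomised. The 72 reproduces as 60 × 1.2 = 72. Dividing by the retention rate gives 60 / (1 − 0.20) = 75. At the plan's own rate, 72 × 0.80 = 57.6 subjects complete, which is below 60. Section 10.7 does not say whether a V2-only subject counts as contributing. If completers are meant, the replacement clause is reached at the planned discontinuation rate. Replacement restores numbers; it does not restore the lost observations. Nothing in the plan deletes the data already collected from the woman replaced.

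**4. Direction of bias.** This is a simulation on assumed data and shows direction only. Inputs from section 10.7: means 25 and 10 mL, SDs 50 and 15 mL, true difference 15 mL, 72 subjects. Assumptions: normal data, within-subject correlation 0 or 0.5, a random-intercept model with one common variance, and 14 women lost between V2 and V3 (about 20% of 72). In the two selective patterns all 14 come from one sequence, which is deliberately extreme. Mean estimates over 400 runs, in mL:

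| Who is lost before V3 | Correlation | All available data | Both visits only |
|---|---|---|---|
| Random | 0 | 15.6 | 15.7 |
| Random | 0.5 | 14.8 | 14.8 |
| Comparator first, highest V2 RV1 | 0 | 14.8 | −0.5 |
| Comparator first, highest V2 RV1 | 0.5 | 12.9 | 1.7 |
| Investigational first, highest V2 RV1 | 0 | 14.9 | 19.6 |
| Investigational first, highest V2 RV1 | 0.5 | 9.5 | 12.1 |

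Estimates restricted to women with both visits fall on either side of 15. The all-available model is much closer to the truth in the comparator-first pattern.

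**5. Why 12.9 and 9.5 are not 15.** Selection there depends only on the observed V2 value, so V3 is missing at random. The shift comes from the common variance. With correlation 0.5 the covariance is 0.5 × 50 × 15 = 375, the average variance is (2500 + 225) / 2 = 1362.5, and the model carries V2 forward with slope 375 / 1362.5 = 0.275. The true slopes are 0.5 × 50 / 15 = 1.67 for an unseen comparator value and 0.5 × 15 / 50 = 0.15 for an unseen investigational value. Missing at random therefore protects the estimate only if the covariance is modelled adequately. Section 10.3 does not mention device-specific variances, although section 10.7 assumes SDs of 50 and 15 mL.

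**The case against.** The strongest reply is that the rule is narrow and may seldom be used. It covers only noncompliance that affects scientific integrity. Home use follows each woman's own regime, no minimum use is set, and no data are collected at home. Deviations are reviewed at V2 and V3, when she is already in the clinic. If home use does not affect RV1 by HCP, poor home use would hardly meet the threshold. Replacement is conditional on discussion with the sponsor, and withdrawal by choice is a separate route that no rewording would change.

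Most of this stands, and it rules out several stronger readings that a reader might infer:
- That women who stop using a device at home lose their V2 or V3 measurement. No section calls stopping a device noncompliance. The loss follows only if an investigator judges it to affect scientific integrity.
- That the FAS becomes a completer analysis. V2-only subjects stay in the FAS and in the mixed model. Only the Wilcoxon test needs both visits.
- That the PP run ceases to be an independent check. It is by definition a subset of the FAS and was never independent.
- That replaced women vanish from the analysis. Nothing says so.

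What the reply does not answer is that, once the judgement is made, withdrawal is mandatory, the threshold is left to people who know the device, and no text preserves the remaining measurement. The perception questionnaire and adverse events do depend on home use, so an investigator could reasonably find the threshold met on those grounds and lose a primary measurement that was still obtainable.

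**Conclusion.** The point holds as a gap in design and wording. Section 6.3 turns some noncompliance into loss of the remaining RV1 measurements, when the plan's other provisions would handle it without that loss.

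The certain size is per subject: both RV1 values if she is withdrawn before V2, one value and the pair if between V2 and V3. The effect on the estimated device difference cannot be derived from the documents. They give no rate of such withdrawals, no split by device and no link between noncompliance and RV1. It could favour either device. The simulated figures rest on extreme assumed selection and are not a forecast.

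The conclusion assumes that the principal investigator knows the allocation, which is inferred from the open-label design and section 5.9, and that the HCP catheterisation usually remains feasible after noncompliance. It does not extend to the separate rule in section 6.4, under which "After randomisation subjects who fail to comply with inclusion or exclusion criteria will be withdrawn from the study". The change is worth making because it is cheap and removes an avoidable source of selection; the point does not by itself invalidate the primary analysis.

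**What to change.** In section 6.3, remove noncompliance from the mandatory withdrawal list and replace it with wording to this effect: noncompliance is recorded as a protocol deviation under section 13; the subject stays in the investigation and attends the scheduled V2 and V3 measurements unless she withdraws consent or the existing safety rule applies; she is analysed in the FAS and excluded from the PP set only. Leave the safety and subject-choice rules as they are.

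In sections 6.3 and 10.7, allow replacement for such a subject to be considered only when no further RV1 value can be obtained, and state that all data already collected from a replaced subject are kept. Say in section 10.7 whether a V2-only subject counts towards the 60.

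The cost is protocol wording and a few more scheduled visits completed by non-adherent subjects. Their RV1 values enter the FAS, and the planned PP run shows the result without them.

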6.4 Screening Failures and Drop-Outs

Subjects that have signed the informed consent form but fail to comply with inclusion or exclusion criteria are considered "screening failures" up until randomisation. After randomisation subjects who fail to comply with inclusion or exclusion criteria will be withdrawn from the study and considered "drop-outs"

6.5 Subject Identification and Confidentiality

Subjects will be identified in the electronic CRF (eCRF) and any other document transmitted to the sponsor by the principal investigator or clinical site staff, by a unique identification number.

Data entered in the eCRF are confidential and will only be available to the sponsor (including sponsor delegates), members of data management teams, the statistician, members of the EC or IRB and if requested to regulatory authorities.

The principal investigator, for each clinical investigation site, will maintain as part of the investigational file a list identifying all subjects entered into the clinical investigation.

7 Procedures

7.1 Catheterisation set-up

Subjects are not allowed to lay down during catheterisation. Only sitting at minimum 45 degrees angle or standing is optional (V1, V2 and V3).

At V2 and V3 it is important to ensure free urine flow from catheter outlet into urine collection container placed on scale. Urine collection container must remain untouched during catheterisation. The scale is connected to the databox, which will record catheterisation profile during catheterisation. If the scale is moved, it must be calibrated. See separate manual for use of the databox.

7.2 Clinical investigation-related procedures

Visit 0 (V0) – Screening:

- Information about investigation, screening and review of Informed Consent Form/Subject Information Form
- Scheduling Baseline Visit (V1) unless performed the same day as Screening Visit (V0)
- Register the potential subject on the Pre-screening Log if not already registered

Visit 1 (V1) – Inclusion, Baseline and introduction to T1:

NB! The subject should not have changed their medication the last 24 hours before V1. If subjects show symptoms of UTI (assessed by investigator), they must be rescheduled.

- Introduction to the investigation reviewed and confirmed
- Informed Consent signed
- Enrolment in the investigation and allocation of subject number
- Check of in- and exclusion criteria
- For female subjects of childbearing potential: urine pregnancy dipstick
- Collect Baseline information:
 - Age [years]
 - Height [cm]
 - Weight [kg]
 - When did you start using a catheter (YEAR + MONTH (if known))
 - Average number of catheters used per day [number]
 - Current primary product
 - Coloplast: SpeediCath Compact Female, SpeediCath Compact Female Plus, SpeediCath Compact Eve
 - Wellspect: Lofric Sense, Lofric Elle
 - Hollister: Infyna Chic, Vapro Pocket
 - B. Braun: Actreen Mini
 - Bard: Hydrosil Rose, Hydrosil GO, Magic3Go
 - Convatec: GentleCath Air Female
 - Curan: Curan Lady, Curan Twist
 - Other (text)
 - Current product size
 - CH12
 - CH14
 - Position most frequently used in catheterisation
 - Sitting
 - Laying
 - Standing
 - Other (text)
 - Urethral sensation
 - Normal
 - Impaired
 - None

- Hypersensitive
- Reason for using intermittent catheterisation
 - Spinal cord injury
 - Multiple sclerosis
 - Spina Bifida
 - Others (as text)
- Neurogenic/Non-neurogenic
- Body mobility / ambulation
 - Walking
 - Walking with difficulty/aids
 - Using a wheelchair
 - Confined to bed
- How is your dominant hand?
 - Right-handed
 - Left-handed
 - Mixed or cross-dominant (i.e., changes according to task)
 - Ambidextrous (i.e., equal ability in both hands)
- How would you describe the level of dexterity of your hands?
 - Left hand
 - Normal dexterity
 - Reduced dexterity
 - Greatly reduced dexterity
 - Don't know
 - Right hand
 - Normal dexterity
 - Reduced dexterity
 - Greatly reduced dexterity
 - Don't know
- Concomitant medication related to urinary function (assessed by principal investigator) and pain management
- Relevant medical history (assessed by the investigator)
- Randomization
- Introduction to 1st randomly assigned product, including IFU.
- Self-catheterisation (with 1st randomly assigned product)
- Catheterisation position noted [Sitting/standing]
- Catheter used for catheterisation noted [investigational product/comparator, including product size (CH12/CH14)]
- Catheter handed out for the first test period is noted [investigational product/comparator, including product size (CH12/CH14)]
- Scheduling Visit (V2), 14 days (+/-3 days) days after Baseline Visit (V1)
- Complete eCRF

Test Period 1 (T1):

The two weeks of home-use with the first randomly assigned product according to an individual usage regime. No data will be collected during the home period.

Visit 2 (V2) – Catheterisation, follow-up and introduction to T2

The subject should not have changed their medication the last 24 hours before V2 or show symptoms of UTI (assessed by investigator). If signs of UTI, they must be rescheduled and registration of AE.

- Ask for change in relevant medical history since last visit.
- Review of Adverse events/Serious adverse events/Adverse device events, Device deficiencies and Protocol Deviations
- Review of changes in concomitant medication
- Assessment on user perception for Test Period 1.

HCP-Catheterisation:

- Pre-catheterisation volume [mL] measured in triplicate with a bladder scanner. All three measurements must be above 150 ml to proceed. If not subject is asked to intake fluid and wait until bladder volume is ≥ 150 ml.
- Catheterisation with the 1st randomly assigned product used in T1 will be performed by HCP. NB! HCP should wait for 3 sec. when suspicion of flow-stop before rotating catheter to make it more clear on the profile from the databox.
- Catheter used for catheterisation [investigational product/comparator, including product size (CH12/CH14)], position [Sitting/standing], and time for start of catheterisation is noted.
- Urine volume at 1st flow stop [g] and post catheterisation [g] is noted.
- Number of flow stops is noted.
- All assessments pertaining to performance, including catheterisation profile, will be recorded at the catheterisation.
- Residual volume [mL] will be measured in triplicate with bladder scanner after catheterisation is completed.
- After first catheterisation subjects will be asked to intake fluid and wait in the waiting room to ensure there is urine in the bladder before the second catheterisation.

Self-Catheterisation:

- Pre-catheterisation volume [mL] measured in triplicate with a bladder scanner. All three measurements must be above 150 ml to proceed. If not subject is asked to intake fluid and wait until bladder volume is ≥ 150 ml.
- Catheterisation with the 1st randomly assigned product used in T1 will be performed by subject. Subject should wait for 3 sec. when suspicion of flow-stop before rotating catheter to make it more clear on the profile from the databox.
- Catheter used for catheterisation [investigational product/comparator, including product size (CH12/CH14)], position [Sitting/standing], and time for start of catheterisation is noted.
- Urine volume at 1st flow stop [g] and post catheterisation [g] is noted.
- Number of flow stops is noted.
- All assessments pertaining to performance, including catheterisation profile, will be recorded at the catheterisation
- Residual volume [mL] will be measured in triplicate with bladder scanner after catheterisation is completed.
- After completed self-catheterisation, subjects are asked to assess any level of discomfort during catheter insertion, during emptying of bladder, at the end of emptying and at withdrawal of catheter (evaluated on the visual analogue scale (VAS) [cm]). VAS scores are asked to be rated immediately after withdrawal of catheter.
- Introduction to 2nd randomly assigned product, including IFU.
- Schedule V3 within 28 days (+/- 3 days) after V1
- Complete eCFR

Test period 2 (T2)

The two weeks of home-use with the second randomly assigned product according to an individual usage regime.

Visit 3 (V3) – Catheterisation, follow-up, and termination

The subject should not have changed their medication the last 24 hours before V2 or show symptoms of UTI (assessed by investigator). If signs of UTI, they must be rescheduled and registration of AE.

- Ask for change in relevant medical history since last visit.
- Review of Adverse events/Serious adverse events/Adverse device events, Device deficiencies and Protocol Deviations
- Review of changes in concomitant medication
- Assessment on user perception for Test Period 2.

HCP-Catheterisation:

- Pre-catheterisation volume [mL] measured in triplicate with a bladder scanner. All three measurements must be above 150 ml to proceed. If not subject is asked to intake fluid and wait until bladder volume is ≥ 150 ml.
- Catheterisation with the 2nd randomly assigned product used in T2 will be performed by HCP. NB! HCP should wait for 3 sec. when suspicion of flow-stop before rotating catheter to make it more clear on the profile from the databox. NB! Position for the catheterisation must be the same as the position for the HCP catheterisation at V2.
- Catheter used for catheterisation [investigational product/comparator, including product size (CH12/CH14)], position [Sitting/standing], and time for start of catheterisation is noted.
- Urine volume at 1st flow stop [g] and post catheterisation [g] is noted
- Number of flow stops is noted
- All assessments pertaining to performance, including catheterisation profile, will be recorded at the catheterisation.
- Residual volume will be measured in triplicate with bladder scanner after catheterisation is completed.
- After first catheterisation subjects will be asked to intake fluid and wait in the waiting room to ensure there is urine in the bladder before the second catheterisation.

Self-Catheterisation:

- Pre-catheterisation volume [mL] measured in triplicate with a bladder scanner. All three measurements must be above 150 ml to proceed. If not subject is asked to intake fluid and wait until bladder volume is ≥ 150 ml.
- Catheterisation with the 2nd randomly assigned product used in T2 will be performed by subject. Subject should wait for 3 sec. when suspicion of flow-stop before rotating catheter to make it more clear on the profile from the databox. NB! The position must be the same as the position for the self-catheterisation at V2.
- Catheter used for catheterisation [investigational product/comparator, including product size (CH12/CH14)], position [Sitting/standing], and time for start of catheterisation is noted.
- Urine volume at 1st flow stop [g] and post catheterisation [g] is noted
- Number of flow stops is noted
- All assessments pertaining to performance, including catheterisation profile, will be recorded at the catheterisation.

- Residual volume [mL] will be measured in triplicate with bladder scanner after catheterisation is completed.
- After completed self-catheterisation, subjects are asked to assess any level of discomfort during catheter insertion, during emptying of bladder, at the end of emptying and at withdrawal of catheter (evaluated on the visual analogue scale (VAS) [cm],). VAS scores are asked to be rated immediately after withdrawal of catheter.
- Terminate subject
- Complete eCRF

Unscheduled visit/call

If an unscheduled call/visit is needed the unscheduled form in the eCRF must be completed.

